## A Gender-enhanced PrEP-Exposure Prophylaxis Information-Motivational Workshop for Young South African Women – Data analysis plan 24 june 2022

### From the original proposal

#### 3.3.9.3 Statistical analysis

**Aim 3a.** Workshops: Compare participants (N=100) randomized to Gender-Enhanced or Information-Only Workshops on undergoing PrEP clinical assessment (primary outcome); uptake of PrEP if eligible, and 3-month PrEP retention (secondary outcomes) and hypothesized mediators (risk perception, gender barriers, self-efficacy, outcome expectancies, PrEP-stigma, attitudes, peer norms, information) post-intervention and at 3-months. To compare the **primary and secondary outcomes** across the two workshop conditions, we will use generalized linear models (GLM) with a logit link function and the method of generalized estimating equations (GEE) to account for the effect of clustering within workshop and clustering within recruitment chain. Intervention condition will be the primary predictor. We will adjust for any substantial baseline differences by group on age. To assess if being a PHA, i.e., talking to other women about HIV prevention serves as an additional intervention dose, a secondary analysis will include a variable for whether the woman served as a PHA and recruited other workshop attendees (yes/no).

For the hypothesized mediators, all of which are summary measures from multi-item scales, we will use GLM with an identity link function and GEE (to account for clustering effects) to compare the mean difference between the two intervention groups from post-test to pre-test, and from 3-month follow-up to post-test, to determine if there is an increase, decrease, or no change over time (difference of difference analysis), adjusting for age if necessary.

Accompanying these tests will be point and interval estimates for parameters of interest. Since our aim is not to estimate proportions (or means) from a theoretically representative population, we will *not* use respondent-driven sampling (RDS) weights; our aim is only to account for the greater similarities of individuals by recruitment and intervention-delivery clusters.

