Power Considerations. The primary goal for this pilot work is to collect preliminary data regarding feasibility, acceptability and target outcomes for the proposed intervention. In line with guidelines from PA-17-166: *Formative and Pilot Intervention Research for Prevention and Treatment*, which caution against using pilot studies (where the sample size is of necessity small) to obtain an estimate of an effect size, we will use these pilot data to rule out unusually large or small true effects through standard 95% confidence interval procedures. We will confirm extrinsic effect sizes are contained within our confidence intervals from the pilot. We will examine the distribution of each variable, and calculate summary statistics by intervention condition. We will estimate key intervention parameters with sample means and proportions together with two-sided 95% confidence intervals, and test the primary null hypotheses at the traditional two-sided level  $\alpha=.05$  (simulation of the subsequent RCT). For planning the RCT, we will also consider one-sided 90% confidence limits for mission-critical *design parameters* such as standard deviations and reference group endpoint rates and proportions in the conservative direction. This is because we intend to plan sample size for the RCT so that power will be “excellent” (at least 80% power) for the clinically relevant effect size to be specified. This strategy will make proper allowance for the limited sample size of the pilot study with its consequent uncertainties, and still yield appropriate sample sizes for the RCT. “Mission-critical” parameters include proportions for dichotomous endpoints (uptake of PrEP clinical assessment, uptake of PrEP yes/no); means and standard deviations for continuous potential mediators of outcome (e.g. gender barriers, PrEP-stigma). Large sample sizes are not required to locate these parameters approximately, but adequately, for planning the subsequent trial, whereas testing the study hypothesis in the pilot

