will generally not have sufficient statistical power. Estimation of mission-critical design parameters with point and confidence interval estimates will be considered highly important; continuous outcome measures make it feasible to detect promising effect effects even in small samples. For the continuous measures, means and standard deviations (sd) will be estimated. For approximately normally distributed variables, an upper one-sided 90% confidence limit for the sd,  $\sigma_u$ , will be constructed from  $\sigma_u = s \chi^2_{v,10}^{1/2}$ , where s is the sample sd and  $\chi^2_{v,10}$  is the upper 10th percentile of the chi-squared distribution with v degrees of freedom. For approximately log-normally distributed variables, a logarithmic transformation will be applied to achieve approximate symmetry and normality. For the dichotomous variables (such as the primary and secondary outcomes, or the PDR performance criteria), exact binomial methods will be employed for the CIs for proportions. As an example, the width of the exact 95% confidence interval around a point estimate of 40% (e.g., percent women who score high-risk) would be 30%-50% with 100 participants.

While testing the primary null hypothesis is not the primary goal for this pilot study, if we assume the proportion of women who undergo PrEP clinical assessment in the information-only group ranges from 20% to 50%, with total sample size of 100 participants we are still able to declare a difference of 33 to 36 percentage points as statistically significant at 0.05 level with power of 80% if the within recruitment chain and within intervention-delivery group correlation coefficient is no greater than 0.1. As an illustration of how this can be used for planning the large randomized trial, suppose in this pilot study, proportion of participants take PrEP risk screening is 85% and 50% for Gender-Enhanced workshop and Information-Only Workshop respectively while the minimally clinically relevant improvement, on extrinsic grounds, is an improvement of 15 percentage points. Then, N=240 per group would be required in the RCT. The above plan will allow us to assess feasibility and acceptability, estimate factors influencing intervention parameters, and examine the range of possible effect sizes for our primary outcome. Therefore, the information collected from this pilot study should put us in an excellent position to conduct a future full-scale RCT.

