## Data Analysis

Workshops: Compare women randomized to the virtual group-interactive workshop with those randomized to individually-accessed links to a PrEP promotional video and PrEP information on the **primary outcome of having an individual discussion with the study nurse about the possibility of taking up PrEP; undergoing HIV self-testing guided by the study nurse (either in-person at the GHRU office or via telehealth visit) (secondary outcome); if eligible for PrEP, initiating PrEP (secondary outcome)**, and, for all women, changes in hypothesized mediators (information, risk perception, gender barriers, outcome beliefs, PrEP-stigma, peer norms) post-intervention and at 3-month follow-up.)

To compare the **primary and secondary outcomes** across the two workshop conditions, we will use generalized linear models (GLM) with a logit link function and the method of generalized estimating equations (GEE) to account for the effect of clustering within recruitment chain. The logit link function is appropriate because the primary and secondary outcomes are dichotomous and characterized as yes/no if achieved at any time over the course of the study by the time of the 3-month follow-up interview. Intervention condition (Gender-Enhanced or Individual Access) is the primary predictor. Although the original data analysis plan also specified accounting for clustering by workshop group attended, we will not account for clustering by workshop group because women in the IA condition received the intervention as individuals rather than as groups.

We will adjust for any substantial baseline differences by condition on age. We will also adjust for any substantial differences by other demographic and behavioral characteristics, such as education level, whether attending school, has a primary partner, sexual risk behaviors (to be defined), relationship power, reported intimate partner violence if these factors differ substantially by condition at baseline and are also associated with the outcome (i.e., meet the conditions of confounding).

To assess if being a PHA, i.e., talking to other women about HIV prevention serves as an additional intervention dose, a secondary analysis will include a variable for whether the woman served as a PHA and recruited other workshop attendees (yes/no).

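### Exact binomial intervals for single proportions ignore the recruitment chains that the SAP allows for elsewhere, so the 30%-50% example holds only if women in a chain are uncorrelated

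*SAP*

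**What the plan says.** The SAP's section 3.3.9.3, under Power Considerations, sets the interval method for binary quantities: "exact binomial methods will be employed for the CIs for proportions". The sentence covers the trial's binary outcomes and the recruitment criteria together, since it opens with "For the dichotomous variables (such as the primary and secondary outcomes, or the PDR performance criteria". The worked example is a reach measure, percent high-risk. It takes an estimate of 40% and says that the interval "would be 30%-50% with 100 participants". For planning the RCT the same section adds that "we will also consider one-sided 90% confidence limits for mission-critical" quantities, and reference-group proportions are among those it lists.

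Clustering is recognised in three other places:

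- Section 3.3.9.3, Aim 3a, declines respondent-driven-sampling weights because "our aim is only to account for the greater similarities of individuals by recruitment and intervention-delivery clusters".
- The detectable-difference statement under Power Considerations holds "if the within recruitment chain and within intervention-delivery group correlation coefficient is no greater than 0.1".
- The current Data Analysis section keeps "the method of generalized estimating equations (GEE) to account for the effect of clustering within recruitment chain" and drops clustering by workshop group.

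Aim 3b treats the reach and recruitment measures as simple proportions, with no model. The exact binomial sentence is carried over from the original proposal, but neither the December 2020 revisions nor the Data Analysis section replaces it.

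**The concern.** Women in this pilot arrive in chains. Sixteen seeds start them, each advocate may bring in up to three women, and advocates recruit only to their own condition, so each chain lies within one arm. Women linked in this way probably resemble one another in risk, in clinic contact and in willingness to speak to the nurse. An exact binomial interval counts them as independent, so it is too narrow whenever the within-chain correlation is positive.

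This matters because the SAP makes estimation, not testing, the main purpose of the pilot. For the reach and advocate-acceptance proportions, which have no model, this interval is the only statement of uncertainty. For the reference-arm outcome rate, the one-sided limit is meant to carry the pilot's uncertainty into the RCT sample size.

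**Working it through.** **Inputs.** From the SAP: 40%, N = 100, ICC no greater than 0.1, reference rates 20%-50%, and a 15-point minimal effect for the RCT. From the protocol (Study Procedures, pilot recruitment and wave table): 16 seeds, then three waves of 28, so 16 + 84 = 100; 1:1 randomisation of seeds; at most 3 recruits per advocate. Derived: mean chain size m = 100/16 = 6.25, with about 8 chains and 50 women per arm. Not in the documents, so assumed: the actual ICC (shown from 0 to 0.1) and the spread of chain sizes.

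**1. The SAP's own figure.** Clopper-Pearson for 40/100 gives 30.3%-50.3%. The stated 30%-50% is correct under independence, and only then.

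**2. With chains.** Design effect DEFF = 1 + (m − 1) × ICC; effective n = 100/DEFF; Clopper-Pearson on the effective n. For unequal chains, DEFF = 1 + [(1 + CV²)m − 1] × ICC. At CV 0.66 and ICC 0.1 this is 1 + (1.4356 × 6.25 − 1) × 0.1 = 1.80.

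| ICC | Chain sizes | DEFF | Effective n | 95% limits around 40% |
|---|---|---|---|---|
| 0 | any | 1 | 100 | 30.3%-50.3% |
| 0.02 | equal | 1.105 | 90.5 | 29.8%-50.8% |
| 0.05 | equal | 1.26 | 79.2 | 29.1%-51.6% |
| 0.1 | equal | 1.525 | 65.6 | 28.1%-52.8% |
| 0.1 | CV 0.66 (assumed) | 1.80 | 55.6 | 27.1%-54.0% |

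At ICC 0.1 with equal chains the width rises from 19.9 to 24.7 points, and 24.7/19.9 = 1.24, so about 24% wider.

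**3. Coverage of the unadjusted limits.** Outcomes were simulated as beta-binomial within chain.

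- Near-equal chains (6 or 7 women), true rate 40%, nominal 95%: 96% at ICC 0, 93% at 0.05, 90% at 0.1.
- The wave plan run as branching chains (recruits shared at random among advocates, at most 3 each, half of recruits becoming advocates; resulting size CV about 0.66), true rates 20%-50%: 96-97% at ICC 0, about 95% at 0.02, 92-93% at 0.05, 87-89% at 0.1.
- One-sided 90% upper limit in one arm (8 chains, about 50 women), ICC 0.1: average 88% with near-equal chains (86-91% by true rate) and 86% with branching chains (83-89%).

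**4. Consequence for the RCT.** The n per group for a 15-point improvement (two-sided 0.05, 80% power, normal approximation) was taken at the largest value within the one-sided 90% limits from 50 women, DEFF 1 against 1.525.

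- Reference rate 20%: the upper limit moves from 29.1% to 31.8%, and n from 161 to 166 (166/161 = 1.03).
- Reference rate 30%: 173 to 174.
- Reference rates 40% and 50%: no change, because the unadjusted limits already include the rate of greatest variance (42.5%, where the two arms straddle 50%).

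**5. The neighbouring power figure.** Detecting a difference with 80% power and 50 per arm needs 26.0-27.6 points under independence. The SAP's 33-36 points needs a DEFF of about 1.65-1.7 (33.3-35.8), or about 1.4 with continuity correction (33.8-35.7). So the detectable difference appears to include a clustering allowance, while the interval in the same section has none.

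**The case against.** The strongest reply is that this affects descriptive intervals in a pilot and little else. Much of it stands.

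- A reader might infer that the between-arm effect intervals, which the SAP uses to exclude implausibly large or small effects, are also too narrow. The documents do not support that. Aim 3a says the GEE tests will be accompanied by point and interval estimates, and the Data Analysis section keeps the GEE clustered by chain. The exact binomial sentence covers proportions.
- A reader might infer that the RCT would be materially undersized. Step 4 shows a change of about 3% at most across the SAP's own range of reference rates. The illustrative 240 per group is not shown to come from these limits.
- The value 0.1 is a ceiling in a power statement and covers chain and delivery group together. It is not an estimate. At ICC 0.02 the example barely moves, and the conservatism of the exact method absorbs the difference.
- The 27%-54% version depends on an assumed spread of chain sizes. The protocol caps recruits to balance chains and adds new seeds if advocates fall short, which would shorten them.
- The SAP disclaims estimating proportions for a representative population. That explains the absence of weights, but the same sentence makes allowance for within-cluster similarity the stated aim, so it does not excuse independent-sample limits.

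What the reply does not remove is the internal inconsistency: dependence is accepted for the model and the power statement and ignored for the intervals, and no later text corrects this.

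**Conclusion.** The point holds for single proportions: arm-level primary and secondary outcome rates, the reach measures, and the percentage becoming advocates. The stated 30%-50% is right only at ICC 0. Over the SAP's own range it widens to about 28%-53% with equal chains, or about 27%-54% with the assumed unequal ones. At the ceiling the nominal 95% interval covers about 87-90% and the one-sided 90% arm limit about 85-88%; at ICC 0.02 or below the effect is negligible. These figures rest on 16 chains, a mean size of 6.25 and a beta-binomial outcome.

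The chain-clustered between-arm analysis is not affected and the RCT planning effect is small, so this is a should-fix and does not undermine the pilot. Separately, the criterion of at least two recruits per advocate is a mean count, so binomial limits do not apply to it.

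**What to change.** In Power Considerations, or preferably in the current Data Analysis section:

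1. Replace exact binomial limits for these proportions with chain-adjusted ones. Two options fit: Clopper-Pearson on the effective sample size from the chain-robust variance, with a t adjustment on chains minus 1 degrees of freedom (Korn-Graubard); or a GEE-intercept interval with a small-sample correction, since there are only about 16 chains, 8 per arm.
2. Use the same method for the one-sided 90% limits on reference-group proportions.
3. Restate the example over a range: about 30%-50% at ICC 0, 29%-52% at 0.05 and 28%-53% at 0.1, noting that unequal chains widen it further.
4. Give recruits per advocate an interval for a mean, also allowing for chains.

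The cost is a few SAP sentences and a few lines of code. No new data or design change is needed. The stated precision becomes slightly less favourable.

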### **December, 2020 Revisions.**

In December, 2020, we revised the specific aims of the study as a consequence of being unable to conduct in-person workshops and therefore shifting to a virtual format. The following is taken from the proposal that was submitted to and approved by our program officer:

Because of the shift to a virtual group workshop, we have also reconceived our comparison condition. Previously, the comparison condition for the gender-enhanced group workshop was an information-only group workshop. However, since the enhanced condition is now the virtual group-based interactive workshop, we believe that an appropriate comparison condition would be individually-accessed web-links without any group interaction. The weblinks will include a PrEP motivational video (also included in the Gender-enhanced condition), a South African government PrEP website, and a South African government contraception options website. PrEP motivational videos have been used in other PrEP studies and PrEP information websites are becoming widely available, making this a reasonable “standard of care” condition. The main study question thus becomes, ***is a virtual group-based gender-enhanced group workshop more effective in prompting women to consider PrEP for themselves than individually-accessed PrEP information and motivation?***

We are also proposing a small change in how we operationalize the study outcome. The original protocol specified that after the workshop, women who were willing to consider PrEP for themselves would be escorted from the workshop location to the Addington Hospital PrEP access site (Pink House) just outside the Hospital clinic. ***Undergoing individual PrEP counseling including HIV-testing*** was the primary study outcome. At this time, asking women to attend a clinic for PrEP counseling is no longer feasible, as many people in South Africa are foregoing care for even more urgent conditions. We have been able to obtain the services of the nurse employed

by the Gender and Health Research Unit of the Medical Research Council to counsel women around PrEP and conduct HIV counseling and testing, either in person at the MRC office or via a telehealth nurse visit. HIV testing will be done using Oraquick®, an MRC-approved HIV self-test kit, either at the MRC office or offsite by the woman herself, with guidance from the nurse. We therefore propose to revise the primary study outcome to the following: ***having an individual discussion with the study nurse about taking up PrEP (either in-person or via telehealth). Undergoing HIV self-testing guided by the study nurse (either in-person at the GHRU office or via telehealth visit) will be a secondary outcome, as will initiating PrEP if eligible for PrEP (HIV-negative).***

These outcomes will be measured as follows: On the post-test assessment, women will be asked if they wish to speak with the study nurse about PrEP (and/or about any other issues). A “yes” response will trigger a notification to project staff, who will inform the study nurse. The study nurse will then contact the individual participant to arrange the counseling session. The study outcome will be considered to have been enacted when the participant has a PrEP counseling session. This, along with the result of PrEP counseling (e.g., underwent HIV testing or not, PrEP-eligible or not, and will initiate PrEP or not), will be documented by the nurse.

The revised specific aims of this study are as follows:

1. **Formative Work (no changes):** To ***inform intervention development*** through
  - a. Focus groups (six) with at-risk AGYW aged 18-25, grouped by age and recruitment venue (community, family planning clinic) to explore knowledge of, beliefs about, motivators for, and concerns about PrEP in the context of gendered relationship dynamics and PrEP-related stigma;
  - b. Qualitative interviews with men (10 known HIV-positive and 10 HIV-negative or of unknown status) who have female partners aged 18-25 to understand men’s views of PrEP and of their partners’ use of PrEP.
2. **Intervention development (revised):** In collaboration with an Intervention Development Working Group (IDWG) of AGYW, to ***develop a virtual group-based Gender-Enhanced PrEP Information-Motivational workshop***, drawing on our formative Aim 1 data and strategies from our prior HIV prevention interventions, ***and to choose a PrEP video and a PrEP informational website for the individual digital access control condition.***
3. **Pilot (revised):** To evaluate acceptability, feasibility, and outcomes of the intervention components:
  - a. Intervention: Compare women randomized to the virtual group-interactive workshop with those randomized to individually-accessed links to a PrEP promotional video and PrEP information on the ***primary outcome of having an individual discussion with the study nurse about the possibility of taking up PrEP; undergoing HIV self-testing guided by the study nurse (either in-person at the GHRU office or via telehealth visit) (secondary outcome); if eligible for PrEP, initiating PrEP (secondary outcome),*** and, for all women, changes in hypothesized mediators (information, risk perception, gender barriers, outcome beliefs, PrEP-stigma, peer norms) post-intervention and at 3-month follow-up.
  - b. Peer-driven recruitment: 1) Assess ***acceptability and feasibility*** of peer-driven recruitment (PDR) using pre-specified performance criteria for acceptance and recruitment (on average  $\geq 50\%$  attendees agree to recruit other women (i.e., become Peer Health Advocates [PHAs] and  $\geq 2$  recruits/PHA enroll in the study); and 2) evaluate ***reach*** of PDR (percent who score high on HIV risk assessment; percent who never tested or never attended family planning).

## Data Analysis

Workshops: Compare women randomized to the virtual group-interactive workshop with those randomized to individually-accessed links to a PrEP promotional video and PrEP information on the **primary outcome of having an individual discussion with the study nurse about the possibility of taking up PrEP; undergoing HIV self-testing guided by the study nurse (either in-person at the GHRU office or via telehealth visit) (secondary outcome); if eligible for PrEP, initiating PrEP (secondary outcome)**, and, for all women, changes in hypothesized mediators (information, risk perception, gender barriers, outcome beliefs, PrEP-stigma, peer norms) post-intervention and at 3-month follow-up.)

To compare the **primary and secondary outcomes** across the two workshop conditions, we will use generalized linear models (GLM) with a logit link function and the method of generalized estimating equations (GEE) to account for the effect of clustering within recruitment chain. The logit link function is appropriate because the primary and secondary outcomes are dichotomous and characterized as yes/no if achieved at any time over the course of the study by the time of the 3-month follow-up interview. Intervention condition (Gender-Enhanced or Individual Access) is the primary predictor. Although the original data analysis plan also specified accounting for clustering by workshop group attended, we will not account for clustering by workshop group because women in the IA condition received the intervention as individuals rather than as groups.

We will adjust for any substantial baseline differences by condition on age. We will also adjust for any substantial differences by other demographic and behavioral characteristics, such as education level, whether attending school, has a primary partner, sexual risk behaviors (to be defined), relationship power, reported intimate partner violence if these factors differ substantially by condition at baseline and are also associated with the outcome (i.e., meet the conditions of confounding).

To assess if being a PHA, i.e., talking to other women about HIV prevention serves as an additional intervention dose, a secondary analysis will include a variable for whether the woman served as a PHA and recruited other workshop attendees (yes/no).

**Mediators.** “Other outcomes” include those measures designed to tap constructs that are hypothesized in our theoretical model to be mediators, i.e., on the pathway between the intervention and the outcome. These are factors that we believe influence the outcome (women considering PrEP for themselves) and that if changed by the intervention will lead to an increase in this outcome. We want to know if these factors are influenced by the gender-enhanced intervention and help explain (mediate) any changes in the main outcomes. These hypothesized mediators, most of which are summary measures from multi-item scales, include PrEP information, perceived risk for HIV, perceived effectiveness of PrEP, positive outcomes of taking PrEP, gendered HIV prevention barriers related to partner disclosure, PrEP-related stigma, normative beliefs, medication beliefs. Please see the related document entitled “Table of pilot study measures 2022 June 22.” for descriptions.

An additional variable—stage of change for adopting PrEP--was added when we revised the study. This will also be considered a mediator, although at 3month followup, the last option of this measure is “I am taking PrEP”. This is the indicator for the outcome of initiating PrEP.

For the mediators, we will first test if the intervention had any effect on them, using generalized linear models (GLM) with an identity link function and GEE (to account for clustering effects) to compare the mean difference between the two intervention groups from post-test to pre-test, and from 3-month follow-up to post-test, to determine if there is an increase, decrease, or no change over time (difference of difference analysis), adjusting for age and other confounders if necessary. As per [name]: the model is of the form:

$E(Y|X,T1,T2)=\text{constant}+b1*X+b2*T1+b3*T2+b4*X*T1+b5*X*T2$ , where X is the intervention indicator, T1 and T2 are post-intervention and 3-month FU indicator respectively. The regression coefficient b4 represents the group difference in change of the outcome Y (i.e., the potential mediators) from pre- to

post-intervention, however, it is b5-b4 (NOT b5) that represents the group difference in change of Y from post-intervention to 3-month FU.

As a second step, we want to know whether, apart from the intervention, any of the hypothesized mediators are associated with the outcomes, e.g., whether women who at pre-test have low PrEP stigma, high perceived risk, low gender barriers for example, were more likely to have a nurse conversation, undergo HIV testing, initiate PrEP. These analyses will be conducted adjusting for intervention condition.

Finally, any mediators that are altered by the intervention will be included in the earlier models testing intervention effects of gender-enhanced intervention on primary study outcomes. A substantial reduction in the estimate of effect for the gender-enhanced intervention once the mediator is included in the model gives evidence that the hypothesized mediator explains in part the effect, i.e., that the intervention worked, for example, by reducing PrEP stigma or increasing risk for HIV.

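### The denominator for PrEP initiation is left open, its 3-month indicator does not match the SAP's own time window, and the final mediation step names no time point

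*SAP*

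**What the plan says.** **Outcome wording.** The SAP's December 2020 revisions list PrEP initiation as a secondary outcome: "as will initiating PrEP if eligible for PrEP (HIV-negative". The Data Analysis section repeats the condition, "if eligible for PrEP, initiating PrEP (secondary outcome", and in the same sentence says that the mediators are compared for all women.

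**How eligibility becomes known.** In the protocol (Study Procedures, PrEP clinical assessment) the nurse tests a woman who wishes to take up PrEP. Under Blood and other Biological Samples, testing is optional and done only for women who choose eligibility screening. The SAP has the nurse record the result of counselling, for example "underwent HIV testing or not, PrEP-eligible or not, and will initiate PrEP or not".

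**Text that leans towards all women.** Primary and secondary outcomes are "characterized as yes/no if achieved at any time over the course of the study", up to the 3-month interview. The last option of the 3-month stage-of-change item, current PrEP use, is singled out: "This is the indicator for the outcome of initiating PrEP". The power section lists "uptake of PrEP clinical assessment, uptake of PrEP yes/no" among the parameters needed to plan the RCT.

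**Sources.** The protocol (Assessment Instruments) says that outcomes are documented by the nurse and at the 3-month survey, and that PrEP use is self-reported at follow-up. The study refers women elsewhere for PrEP and does not supply it.

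**Mediation.** In the last step, "any mediators that are altered by the intervention will be included in the earlier models" for the primary outcome. No measurement time is given.

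**The concern.** Three gaps could affect the result.

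1. **Denominator.** Whether a woman is known to be eligible depends on two steps after assignment, the nurse discussion (the primary outcome) and HIV testing (a secondary outcome). If the gender-enhanced (GE) workshop works, it changes who reaches them. Comparing initiation only among women known to be eligible then compares differently selected groups, and leaves out the gain from bringing more women to testing.
2. **Indicator.** Current use at 3 months misses a woman who started and stopped, although the SAP counts an outcome reached at any time. The nurse's note that a woman will initiate is an intention, because the start happens elsewhere.
3. **Mediator timing.** The nurse discussion follows the post-test. A 3-month score can therefore be a consequence of the discussion, and adjusting for it can look like mediation.

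At stake are one secondary comparison, the initiation rate carried into RCT planning, and the reading of the mediation analysis.

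**Working it through.** **Inputs.** The documents give no initiation rate and no testing rate for the revised design, so the figures below are illustrations. The testing shares come from a supposition in the SAP's power section, "proportion of participants take PrEP risk screening is 85% and 50% for Gender-Enhanced workshop and Information-Only Workshop respectively", written for the earlier outcome and comparator. Here they are assumed to be the shares tested and found eligible. Initiation of 60% among testers is also assumed. The SAP's one sample size tied to that supposition, 240 per group, reproduces for 50% v 65% at two-sided 0.05 with 90% power and a continuity correction. It does not involve initiation and is not in dispute.

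**Step 1: denominator.** Let t be the share tested and eligible in each arm, p1 the initiation rate among women who would test in either arm, and p2 the rate among women who test only because of GE. With no direct effect of GE on p1:

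- All women: difference = (t_GE − t_IA) × p2
- Eligible only: difference = [t_IA × p1 + (t_GE − t_IA) × p2] / t_GE − p1

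Main case, t = 0.85 v 0.50 and p1 = p2 = 0.60:

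- All women: GE 0.50 × 0.60 + 0.35 × 0.60 = 0.51; IA 0.50 × 0.60 = 0.30; difference +21 points.
- Eligible only: 0.51 / 0.85 = 0.60 against 0.60; difference 0.

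Results over a range of p2 (p1 = 0.60):

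| Testing GE v IA | p2 | Eligible only | All women |
|---|---|---|---|
| 85% v 50% | 80% | +8.2 | +28 |
| 85% v 50% | 60% | 0 | +21 |
| 85% v 50% | 40% | −8.2 | +14 |
| 85% v 50% | 20% | −16.5 | +7 |
| 65% v 50% | 60% | 0 | +9 |
| 65% v 50% | 40% | −4.6 | +6 |

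With equal testing in the arms there is no distortion. A change of sign needs p2 below p1.

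**Step 2: planning value.** With 50 women per arm (half of 100), the IA arm of the main case has 25 known eligible and 15 starters. The rate is 15/25 = 60% (exact 95% CI 39% to 79%) or 15/50 = 30% (18% to 45%), depending only on the denominator.

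**Step 3: indicator.** If 30% of starters had stopped by 3 months (assumed, equal in both arms), current use would be 0.7 × 51 = 35.7% v 0.7 × 30 = 21.0%. The difference is +14.7 points instead of +21.

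**Step 4: mediator time point.** Take a nurse discussion rate of 85% v 50%, so the log odds ratio is b = logit(0.85) − logit(0.50) = 1.735. Let the 3-month score be M = d·X + g·Y + N(0,1), where X is GE, Y is the discussion, and M has no influence on Y. By Bayes' rule, the logistic model of Y on X and M has arm coefficient exactly b − g·d.

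- d = 0.5, g = 0.5: 1.735 − 0.25 = 1.485, a 14% drop.
- d = 0.5, g = 1.0: 1.735 − 0.50 = 1.235, a 29% drop.
- d = 0 or g = 0: no drop.

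The first two drops would be read as mediation although there is none. In simulation, a post-test score gave 0 to 0.1%.

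**The case against.** The strongest reply is that the SAP never specifies a model restricted to eligible women. It compares women by condition, codes the outcome yes or no, and names a 3-month item with no eligibility filter attached. The condition may simply acknowledge that only HIV-negative women can be referred to start PrEP. Because eligible is glossed as HIV-negative, it may also mean excluding only women found to be HIV-positive, and then the testing gap in Step 1 would not drive the result. This stands: the documents do not support a claim that the SAP commits to the eligible-only analysis. They do leave the choice open, and one sentence contrasts the eligible with all women.

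A reader might also infer that a reversed result is to be expected. The documents do not support that either. Reversal needs the extra GE testers to initiate less often than the others, and the protocol ties testing to a wish to take up PrEP, which makes low initiation among testers less likely. The zero in the main case needs no such assumption. It is also true that this zero correctly describes equal initiation among testers, and that the gain would still show in the testing outcome. It would not show in the initiation outcome.

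On sources, the nurse's record of intended initiation stands in a list of examples, and the protocol says both the nurse and the 3-month survey document outcomes. What remains is the lack of a rule for combining them and the mismatch between current use and any-time use.

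On mediation, the SAP does not say that 3-month scores will be used; it does not exclude them. The apparent mediated share arises only if both GE and the discussion shift the score.

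Finally, this is a pilot with limited power. With 42 v 25 known eligible, a difference of about 8 points (52% v 60%) has a 95% half-width of 1.96 × √(0.52×0.48/42 + 0.60×0.40/25) ≈ 24 points.

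**Conclusion.** The concern holds as an ambiguity with a material consequence under one permitted reading. At least three denominators fit the text: all women, all except those found HIV-positive, and only those known to be eligible. The last would miss an effect that works through testing, 0 against +21 points in the main case. That size rests on borrowed testing shares and an assumed 60% initiation rate; with testing at 65% v 50% it is 0 against +9. Reversal is possible but less likely.

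The indicator mismatch holds on the text alone; its size depends on how many women stop before 3 months. The mediation gap also holds, and its size depends on effects that the documents do not give.

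The primary comparison is unaffected. For a secondary outcome in a pilot, severity is low to moderate.

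**What to change.** 1. **Initiation.** State that initiation by 3 months is analysed in all women by assigned condition (recruits take the condition of the woman who referred them). Count as initiated any self-reported PrEP use since the intervention, from the 3-month item or the follow-up questions on PrEP use, or a start documented by the nurse. Do not count a record of intended initiation alone. Women untested or ineligible count as not initiated unless they report use. Report by arm how many women have no 3-month data, with a sensitivity range, for example from none to all of them having initiated. Give the proportion among women known to be eligible, with its denominator, as description only.
2. **Mediation.** In the final step, enter immediate post-intervention mediator values, which precede the nurse discussion.

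**Cost.** A few sentences in the SAP and modest extra analysis, using sources that the protocol already plans. Whether women who started and stopped can be identified depends on the survey's PrEP-use questions, which should be checked. The absolute initiation rate will look lower, and post-test mediators miss changes that appear only later.
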